5.0 PROGRAM OBJECTIVE(S)

5. 1. Study Objectives:

Animal (*in vitro*)-part of the study:

1. To determine changes of macrophage phenotype and macrophage plasticity in mice, particularly C57/BL6 genetic strain after exposure to gastric refluxate (human origin)
2. To determine changes of macrophage phenotype and macrophage plasticity in mice, particularly C57/BL6 genetic strain after exposure to biliary refluxate (human origin)

3. To determine changes of macrophage phenotype and macrophage plasticity in mice, particularly C57/BL6 genetic strain after exposure to duodenogastric/mixed refluxate (human origin).

Clinical (patients) part of the study

1. To investigate blood and biopsy-origin monocyte/macrophage phenotype in patients with different forms of acid reflux disease (non-erosive GERD (NERD), erosive GERD and complications thereof: Barrett's esophagus)
2. To investigate types of refluxate (gastric, biliary, duodenogastric/mixed) in patients with different forms of acid reflux disease (non-erosive GERD (NERD), erosive GERD and complications thereof: Barrett's esophagus)
3. To investigate the relationship between clinical assessments (FSSG questionnaire) and measurements obtained from esophageal pH-impedance monitoring and esophageal high-resolution manometry.

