5.2. Primary Endpoint

Animal (*in vitro*) part of the study:

To determine changes in macrophagal phenotype from baseline after exposure to three different forms of refluxate (gastric, biliary duodenogastric/mixed) by means of assessing:

- a) Morphological characteristics (quantity of M1 (round forms) and M2 (fibroblasts-like) macrophages on 100 analyzing cells in 5 non-interfering sights).
- b) Macrophagal phagocytosis activity (mean percentage of phagocytizing cells in all peritoneal macrophagal cells and mean number of bacteria ingested by macrophages)
- c) Secretory activity (ratio of proinflammatory M1 cytokines IL-1 β , IL-8, IL-12p70, IFN γ , TNF α and TNF β to anti-inflammatory M2 cytokines IL-4, IL-5 и IL-10, as well as M1/M2 cytokines IL-2 и IL-6).

- d) Receptor characteristics (ratio of superficial markers CD80 and CD 25 (M1-markers) and CD206 and CD163 (M2-markers). Changes in M1 and M2 ratios determined on the base of receptors will also be analyzed.

Clinical (patients) part of the study:

- 1. Characteristics of blood and biopsy-origin monocyte/macrophage phenotype (morphology, receptor characteristics) in patients with different types of acid reflux disease (NERD, erosive GERD) and complications thereof: Barrett's esophagus).
- 2. Number of patients with gastric, biliary, duodenogastric/mixed refluxate within each of the different patient groups (NERD, erosive GERD and complications thereof: Barrett's esophagus).
- 3. Mean FSSG scores (acid reflux related symptoms, dysmotility symptoms) in patients with gastric, duodenogastric/mixed reflux related to the three different patient subgroups (NERD, erosive GERD and complications thereof: Barrett's esophagus).

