6.2. Number of subjects to be enrolled

Animal (in vitro) Part of the study:

M1 macrophages from mice of genetic line C57/BL6 (90±15 mice) – 90±15 samples
i.e. number of laboratory sockets: 180±30 (90±15 samples in double)

Clinical (patients) Part of the study:

30±5 patients with non-erosive GERD (NERD, as confirmed by endoscopy)

30±5 patients with erosive GERD

30±5 patients with Barrett's oesophagus

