6.5. Program Conduct

[figure not shown]
This is a prospective, experimental study consisting of the two parts: a clinical (patients) part and an animal (in vitro) part.

The clinical (patients) part of the study will be conducted at the Propaedeutic Clinic of Internal medicine, Gastroenterology, Hepatology of First MGMU n.a. IM Sechenov.

The animal part of the study (in vitro) will be conducted at the Moscow State University of Medicine and Dentistry.

The in vitro part of the study will be conducted in M1 macrophages from mice of genetic line C57/BL6 (90 ± 15 mice). To mirror the design of clinical part of the study and to ensure compliance with the enrolled patients' number macrophages from 30 ± 5 mice will be exposed to acid refluxate, macrophages from another 30 ± 5 mice – to biliary refluxate and from the other 30 ± 5 mice – to mixed refluxate.

Figure 1. Study design

	Visit 1	Visit 2	Visit 3	Visit 4	Visit 5
Timelines and Allowance Window	Day 1 Baseline	Day 2 (±1Day)	Day 3 (±2 Days)	Day 4 (±2 Days)	Day 5
Signed informed consent	X				
Assignment of patient identification number	X				
Inclusion and exclusion criteria assessment	X				
Allocation to the subgroups of GERD			X		
Demographics (date of birth, gender, race)	X				
Medical history	X				
Physical examination	X	X	X	X	X
FSSG assessment	X				
Blood sampling (macrophages)		X			
Hematology (RW, HIV, HbsAg, HCV)		X			
Upper gastrointestinal endoscopy with biopsy and collection of refluxate			X		
24-h esophageal pH-impedance test with esophageal high-resolution manometry				X	
Safety assessments*	X	X	X	X	X

* Any safety issues related to the invasive study procedures

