C57/BL6 mice selected for the study would be of an appropriate genetic strain and quality, and the minimum number of animals required to obtain scientifically valid results will be defined according to the number of patients. Mice will be housed in the accredited vivarium of Moscow State University of Medicine and Dentistry to ensure that the general health of the animals is safeguarded and that undue stress is avoided. Special attention will be given to the space

allocation for each animal, and adequate standards of hygiene should be maintained as well as protection against predators, vermin, and other pests. Facilities for quarantine and isolation will be provided. Entry should normally be restricted to authorized persons. Environmental needs such as temperature, humidity, ventilation, lighting, and social interaction will be consistent with the needs of the species concerned. Noise and odor levels will be minimal. Proper facilities will be provided for the disposal of animals and animal waste. Animals will receive a supply of foodstuffs appropriate to their requirements and of a quality and quantity adequate to preserve their health, and they will have free access to potable water, unless the object of the experiment is to study the effects of variations of these nutritional requirements. Veterinary care, including a programme of health surveillance and disease prevention, will be available. Sick or injured animals should, according to circumstances, either receive appropriate veterinary care or be painlessly killed.

All mice will be infused 2 ml of 4% thioglycolates 4 days before the experiment starts. All mice will receive etherization before the experiment. Peritoneal macrophages will be isolated from peritoneal fluid of C57/BL6 mice. Peritoneal lavage fluid will be centrifuged for 4 minutes - 1000 rpm, then supernatant and cell pellet will be divided. Peritoneal macrophages will be cultured in RPMI1640 culture medium with 10% fetal bovine serum (FBS) and 100 U/ml penicillin and 100 µg /ml streptomycin on 48-well plate by 0.5×10^6 macrophages/well.

In vitro experiments on animal biological material (according to GLP and International Guiding Principles for Biomedical Research Involving Animal).

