The functional macrophage phenotype was estimated by cytokine (pro-inflammatory, such as IL-12 (M1 markers) and anti-inflammatory, such as IL-10 (M2 markers)) production [22]. Cytokine concentrations will be defined by flow cytometry [Beckman Coulter FC500, USA] with multiplex definition kits. The functional phenotype of macrophage population will be estimated as a ratio of functional markers of M1 and M2 phenotypes.

Determination of macrophage phenotype after exposure to human acid refluclate, human biliary refluclate and mixed human refluclate will be performed by the above mentioned methods (the part of "Determination of macrophage phenotype") and the changes vs initial results will be registered.

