***In vitro* experiments on human biological material (according to GLP, GCP):**

Isolation and cultivation of macrophages. Macrophages will be isolated from biological material (blood) or derived from blood monocytes. Macrophages will be resuspended in RPMI-1640 nutritional medium. Then the concentration of cells in RPMI 1640 will be adjusted to reflect a concentration of 1×10^6 /ml. [11]. After macrophage isolation the degree of macrophage survival should not be less than 95% (standard technique with trypan blue). The cell suspension will be distributed in a 48-well plate, with each well containing an expected 0.5×10^6 cells per well containing 0.5 ml of RPMI 1640 medium. Macrophage cultivation will be carried out at 37°C and 5% CO₂.

Determination of macrophage phenotype will be performed using the same methods as for animal biological materials.

Macrophage plasticity will be defined by standard criteria similar to macrophage phenotype detection. We will use the definition of morphological phenotype (ordinary light microscope with magnification power 15x40), receptor phenotype (percentage of expression of superficial and cellular receptors - CD80 for M1 phenotype and CD206 for M2 phenotype [12, 13], in the isolated macrophages during flow cytometry by means of CD80 and CD206 monoclonal antibodies [Beckman Coulter, USA; BD Pharmingen, USA].) and functional phenotype (NO and cytokine (pro-inflammatory, such as IL-12 (M1 markers) and anti-inflammatory, such as IL-10 (M2 markers)) production [22]. After determining the macrophage phenotype (see «Determination of macrophage phenotype»), the phenotypic plasticity (PhP) will be calculated. PhP of M1 will be calculated as percent change in the M1/M2 ratio under the action of M1 reprogramming factors and PhP of M2 will be calculated as percent change in the M2/M1 ratio under the action of M2 reprogramming factors. The phenotype marker ratio in standard culture conditions (10% FBS) will be taken as 100%.

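### The animal primary endpoint is change from an initial reading with no time-matched unexposed well tied to it, so each refluxate's change includes any drift in culture

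*Combined protocol and SAP*

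**What the plan says.** Section 5.2 states the animal primary endpoint as: "To determine changes in macrophagal phenotype from baseline after exposure to three different forms of refluxate". It is read through morphology, phagocytosis, cytokine secretion and surface receptors. Section 6.6 (in vitro experiments on animal material) repeats the comparison: phenotype is determined after exposure to each refluxate and "the changes vs initial results will be registered".

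Section 6.5 divides all the mice among the three refluxates, 30 ± 5 to each ("mice will be exposed to acid refluxate, macrophages from another" 30 ± 5 to biliary, and the rest to mixed). Section 6.2 plans 180 ± 30 wells, described as 90 ± 15 "samples in double", and gives neither well of a pair a role.

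Section 6.4.2 gives, for each sample, 48 hours of culture and 24 hours of phenotype assessment, and then a total of 36 hours.

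The nearest thing to an untreated reference is in the part of Section 6.6 on human material. Phenotypic plasticity of M1 is the "percent change in the M1/M2 ratio under the action of M1 reprogramming factors", M2 is treated likewise, and "The phenotype marker ratio in standard culture conditions (10% FBS) will be taken as 100" per cent.

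Section 9.0 calls the study exploratory with no hypothesis tested. It names Student's t-test (paired or not is unstated) or Mann-Whitney for independent samples, and labels p ≤ 0.05 statistically significant.

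**The concern.** The three animal objectives in Section 5.1 ask what each refluxate does to macrophage phenotype. Cultured cells may change between an initial and a later reading whether or not refluxate is added. If the only comparator is the initial reading, that drift is counted as refluxate effect. It can create an apparent effect, or hide a real one if it runs the other way.

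A larger sample or a different test does not remove this, because the error is in what is compared. The remedy is a reading on cells from the same mouse that differs only in exposure. The text does not attach such a reading to the refluxate endpoint. It also does not say which wells or cells supply the initial result, when that result is taken, or when exposure starts and ends.

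**Working it through.** **1. The plan's own counts.** Mice: 3 × (30 ± 5) = 90 ± 15. Wells: 2 × (90 ± 15) = 180 ± 30. Both reproduce. Every mouse is in a refluxate group.

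**2. The plan's own times.** 48 + 24 = 72 hours in sequence; with complete overlap, max(48, 24) = 48 hours. The stated 36 hours fits neither. This is a separate inconsistency, and the point below does not depend on it.

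**3. The bias.** Let τ be the refluxate effect and δ the drift between the two readings.
- Expected (exposed − initial) = τ + δ, so the bias is δ.
- Expected (exposed − unexposed at the same time) = (τ + δ) − δ = τ.
- Difference in change between refluxates A and B = (τA − τB) + (δA − δB). The last bracket is zero if both follow one schedule.

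This step needs no assumed figure.

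**4. Illustration of the consequence.** The documents give no drift, SD or correlation. Assumed: SD 1, correlation ρ = 0.5 between readings from one mouse, n = 30 per refluxate, two-sided 0.05, τ = 0, drift 0.1 to 0.5 SD. For the paired t-test the noncentrality is δ√n / √(2(1 − ρ)) with n − 1 degrees of freedom; at δ = 0.5 this is 0.5 × √30 / 1 = 2.74. The other two tests were simulated, because they ignore the correlation (200,000 runs for t, 40,000 for Mann-Whitney).

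| Drift (SD) | Paired t | Independent t | Mann-Whitney |
|---|---|---|---|
| 0.1 | 0.083 | 0.015 | 0.015 |
| 0.2 | 0.185 | 0.048 | 0.048 |
| 0.3 | 0.355 | 0.131 | 0.123 |
| 0.4 | 0.563 | 0.275 | 0.258 |
| 0.5 | 0.754 | 0.470 | 0.434 |

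Sensitivity:
- At drift 0.5, n = 25 and n = 35 give 0.670 and 0.820 (paired), and about 0.38 and 0.56 (independent t).
- The low independent-test rates at small drift are not general. With ρ = 0 and n = 30 the rate is already 0.067 at 0.1 SD. With ρ = 0.5 and n = 35 it is about 0.057 at 0.2 SD.
- Masking: a real effect of 0.5 SD against a drift of −0.3 SD leaves a net shift of 0.2 SD. It is detected with probability 0.048 instead of 0.470 (independent t), or 0.185 instead of 0.754 (paired).

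**5. The alternatives under the same assumptions.** Exposed minus time-matched unexposed, paired, rejects at 0.049 to 0.051 for drifts of 0.1 to 0.5 SD. The same comparison with an independent-samples t-test rejects at only 0.006, so the paired analysis matters. The contrast between two refluxates rejects at 0.050 when drift is equal.

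**The case against.** **A control may have been intended.** The 10% FBS reference is an untreated condition. Section 5.1 makes plasticity an animal objective ("To determine changes of macrophage phenotype and macrophage plasticity in mice"), and the culture description in Section 6.6 names 10% FBS only for the mouse cells. The reference may therefore have been meant for the mouse work, with refluxate as the stimulus. The duplicate wells in Section 6.2 could also be one exposed and one unexposed. Both readings are possible. Neither is written down: the reference is tied to reprogramming factors, not to refluxate, and has no time, and the plainer reading of the paired wells is technical duplicates.

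**The design figure is missing from the available copy.** Section 6.5 has a figure that is not shown, and it could describe the in vitro arms. A reader might infer that the study has no control, or that its data will be unable to separate refluxate from time in culture. The documents do not support that. They leave the comparator unspecified, and the confounding follows only if the endpoint is run as the text has it.

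**The refluxates control one another.** This stands for contrasts between them. Section 6.4.2 gives one set of durations for every sample, and nothing suggests schedules that differ by group, so a claim of unequal drift would be speculation. Exposure time itself is still not fixed, and such contrasts do not give each refluxate's own change, which is the stated endpoint.

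**The study is exploratory and this part is in vitro.** That lowers the consequence. It does not remove the bias in the stated endpoint, and p ≤ 0.05 will still be labelled significant.

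**Conclusion.** The concern holds for the endpoint as written. A within-refluxate change from the initial reading estimates the refluxate effect plus culture drift, and the available text ties no time-matched unexposed well to it. The bias equals the drift, of unknown size. That result rests only on the endpoint definition and the allocation of every mouse to a refluxate. The false-positive rates (0.083 to 0.754 paired, 0.015 to 0.470 independent t, for drifts of 0.1 to 0.5 SD) are illustrations under assumed drift and correlation, not forecasts. Comparisons between refluxates are not affected if one schedule applies throughout. The change should be made, but confidence is moderate, because a control may have been intended and the design figure could not be seen. The 36-hour total is a separate and definite internal error.

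**What to change.** For each mouse, keep an unexposed well in the same medium for the same time. Define the primary change as exposed minus unexposed and analyse it as paired data. State one exposure interval and one reading time for all three refluxate groups. If the 10% FBS reference or the second well was meant as this control, say so, give its timing and define the endpoint against it; the cost is then wording only.

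Otherwise:
- Using one of the two planned wells as the control adds no wells or cells, but the technical duplicate is lost.
- Keeping the duplicate adds 90 ± 15 wells (single control) or 180 ± 30 (duplicate control), with their assays. At 0.5 × 10^6 cells per well, the need per mouse rises from 2 × 0.5 = 1.0 × 10^6 to 3 × 0.5 = 1.5 × 10^6 or 4 × 0.5 = 2.0 × 10^6, not counting any cells used for a separate initial reading.

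No extra mice are needed if the yield per mouse suffices; the documents do not give the yield.

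Separately, reconcile Section 6.4.2: 48 hours of culture and 24 hours of assessment need at least 48 hours, not 36.

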9.0 STATISTICAL METHODS

This is an experimental, interventional, non-randomized study. The primary purpose of the this study is exploratory in its general sense and no hypothesis is being tested, therefore no sample size calculation was performed.

Planned enrollment in this study constitutes 90 patients in clinical part and 90 subjects (mice) in animal (in vitro) part.

Statistical analysis will be performed using the STATISTICA 8.0 software for Windows (StatSoft Inc, the USA).

Normality of data distribution will be tested by using either the Shapiro-Wilk or Kolmogorov-Smirnov test.

In case of normal (Gaussian) distribution of data significance of differences will be determined by Student's t-test. In cases with non-normal distribution we will use non-parametrical U-test according to the method of Mann-Whitney for independent samples.

Tests resulting in p-values less than or equal to 0.05 will be reported as "statistically significant».

Continuous data will be summarized using descriptive statistics, and the following parameters will be reported: number of observations (n), mean and standard deviation (SD); minimum (Min), and maximum (Max); median. 95 % CI will be calculated.

Categorical data will be presented using frequency (n) and percentage (%).

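### The animal endpoint is change from baseline and only unadjusted tests are named; any comparison of refluxate types would be at least as precise, usually more so, with the initial value as a covariate.

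*Combined protocol and SAP*

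**What the plan says.** Section 5.2 sets the animal primary endpoint: "To determine changes in macrophagal phenotype from baseline after exposure to three different forms of refluxate". It is assessed by morphology, phagocytosis, cytokine secretion and receptor markers. Section 6.6 repeats the before/after structure for the mouse material: after exposure, "the changes vs initial results will be registered". It does not say whether change is an absolute difference, a ratio or a percentage. A percent-change scale is defined only for plasticity, in the part of Section 6.6 on human material.

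The refluxate types use different animals. Section 6.5 says that "macrophages from 30 ± 5 mice will be exposed to acid refluxate", with two further sets of the same size for biliary and mixed refluxate.

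Section 9.0 gives the tests. For normal data, "significance of differences will be determined by Student's t-test", without saying paired or unpaired. Otherwise, "In cases with non-normal distribution we will use non-parametrical U-test according to the method of Mann-Whitney for independent samples". No model with a covariate appears anywhere. Section 9.0 also says that the study is exploratory, that no hypothesis is tested and that no sample size was calculated.

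**The concern.** The hypothesis in Section 4.0 is that different refluxates drive macrophages towards different phenotypes, which is a contrast between types. With change from baseline as endpoint, independent sets of mice per type and two unadjusted tests on offer, that contrast would most naturally become a t-test or U-test on change scores.

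A change score subtracts the whole initial reading, including its measurement noise, whether or not that reading predicts the later one well. A covariate subtracts only the part that predicts. If the initial and exposed readings of a mouse correlate modestly, the difference in precision is substantial.

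What is at stake is information from the one part of the study in which the experimenter sets the exposure. Section 6.6 ties the number of animals to the minimum needed for valid results, so an analysis that draws less from each animal works against that aim.

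**Working it through.** **Inputs from the documents**
- 30 mice per type (Section 6.5; range 25 to 35), with different mice in each type.
- Significance level 0.05 (Section 9.0; two-sided is assumed, since sidedness is not stated).
- No SD, effect size, correlation or power figure is given, so there is no figure of the plan's own to reproduce.

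**Assumptions**
- σ0 and σ1 are the SDs of the initial and exposed values within a refluxate type, and ρ is their correlation within that type. ρ is varied.
- The true difference between two types is set at 0.6 SD of the exposed value, for illustration only.
- Change is a simple difference on the analysis scale, which includes a difference of logs. These formulas do not describe percent change.

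**Step 1. Variance per mouse**
- Exposed value alone: σ1²
- Change: σ0² + σ1² − 2ρσ0σ1
- Adjusted for the initial value (ANCOVA): σ1²(1 − ρ²)

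The second minus the third is σ0² − 2ρσ0σ1 + ρ²σ1² = (σ0 − ρσ1)². This is never negative, so apart from one degree of freedom change cannot be more precise than adjustment. The two tie only when σ0 = ρσ1.

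**Step 2. Equal SDs (σ0 = σ1 = 1)**

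The ratio of change to ANCOVA variance is 2(1 − ρ)/(1 − ρ²) = 2/(1 + ρ). Power is from the noncentral t distribution with 30 per type and 58 df; the noncentrality is 0.6/√(variance × 2/30).

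| ρ | Variance, change | Variance, ANCOVA | Ratio | Power, change | Power, ANCOVA |
|---|---|---|---|---|---|
| 0.2 | 1.60 | 0.96 | 1.67 | 44% | 65% |
| 0.3 | 1.40 | 0.91 | 1.54 | 49% | 67% |
| 0.5 | 1.00 | 0.75 | 1.33 | 63% | 75% |
| 0.7 | 0.60 | 0.51 | 1.18 | 84% | 89% |
| 0.8 | 0.40 | 0.36 | 1.11 | 95% | 97% |

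The exposed value alone has variance 1 and gives 63% power at every ρ. Using 57 df for the covariate leaves the rounded figures unchanged.

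A simulation of three groups of 30 with a pooled slope (10,000 runs) gave variances for change and ANCOVA of 1.40 and 0.91 at ρ = 0.3, 1.01 and 0.77 at ρ = 0.5, and 0.61 and 0.52 at ρ = 0.7. These agree with the formulas.

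**Step 3. Unequal SDs at ρ = 0.5**
- Exposure doubles the SD (σ0 = 1, σ1 = 2): change 1 + 4 − 2 = 3.0; ANCOVA 4 × 0.75 = 3.0. There is no gain.
- Initial SD 1.5 times the exposed SD (σ0 = 1.5, σ1 = 1): change 2.25 + 1 − 1.5 = 1.75; ANCOVA 0.75. The ratio is 2.33.

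**Step 4. When is change worse than ignoring the initial value?**

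Change is noisier than the exposed value alone when σ0² − 2ρσ0σ1 > 0, that is, when ρ < σ0/(2σ1). The cut-off is 0.5 with equal SDs, 0.25 if exposure doubles the SD, and 0.75 if the initial SD is 1.5 times the exposed SD.

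**The case against.** The strongest objection is that the plan never says that types are compared on change. The sentence in Section 6.6 says only that changes are recorded. The animal objectives in Section 5.1 come one per type, the first being "To determine changes of macrophage phenotype and macrophage plasticity in mice, particularly C57/BL6 genetic strain after exposure to gastric refluxate", and none is worded as a contrast. Student's t-test could be meant as a before/after test within a type, which this point does not touch. This stands as a limit: a reader might infer that a comparison on raw change is prespecified, and the documents do not support that. The inference remains reasonable, because the hypothesis is a contrast between types, the only non-parametric test named is for independent samples, and no paired alternative to it is given.

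A reader might also infer that change scores are worse than ignoring the initial value whenever ρ is below 0.5. That cut-off needs equal SDs, which the documents do not establish. An exposure intended to shift phenotype may well alter the spread.

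The study is exploratory, with no power target to miss, and the 0.6 SD difference is an assumption. This is fair and limits the weight of the point. However, Section 9.0 also provides that "Tests resulting in p-values less than or equal to 0.05 will be reported" as statistically significant, so tests will be run and their precision matters.

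Finally, Section 6.2 gives the "number of laboratory sockets: 180±30 (90±15 samples in double"), without saying whether a mouse's two wells are replicates or an unexposed/exposed pair. A fix that presumes two exposed wells to average might not fit. The remedy has to work with one exposed value per mouse, and ANCOVA does.

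**Conclusion.** The point holds in a limited form. The plan defines the animal endpoint as change from baseline, leaves the scale of change undefined for mouse material, does not say how types are compared, and names no baseline-adjusted analysis. If types are compared, adjustment for the initial value is at least as precise as change at any correlation and any SD ratio, apart from one degree of freedom.

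The size of the gain is uncertain. With equal SDs and a 0.6 SD difference, both assumed, it runs from about 21 percentage points of power at ρ = 0.2 to about 2 points at ρ = 0.8. It can be zero if exposure raises the SD, and larger if exposure lowers it.

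The loss is of precision only. No bias or inflated error rate follows, provided mice are assigned to refluxate types without regard to their initial reading. Section 9.0 calls the study non-randomized and no method of assigning mice is given, so that condition should be confirmed. This is a free improvement, not a flaw that invalidates the analysis.

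**What to change.** In Section 9.0, state that refluxate types are compared by ANCOVA:
- **Outcome:** the post-exposure log M1/M2 value, one per mouse, averaging exposed wells if there is more than one.
- **Factor:** refluxate type.
- **Covariate:** the same mouse's initial log M1/M2 value.
- **Report:** adjusted differences between types with 95% confidence intervals.
- **If residuals are clearly non-normal:** a rank-based ANCOVA.

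Keep change from baseline as a descriptive summary and state its scale. Say in Section 6.2 or 6.6 which well supplies the initial value, and that mice are assigned to types without regard to it.

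The analysis costs one degree of freedom and a short addition to Section 9.0. It needs no further animals, and no further measurements as long as the initial value is recorded for each mouse, which the before/after endpoint already requires.
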